8.2.2.2. Overall Survival (OS)

OS is defined as the time from the date of first dose until death due to any cause and will be calculated in months as follows:

$$\text{OS (months)} = [\text{date of death or censoring} - \text{date of first dose} + 1] / 30.4375$$

Survival status is expected to be collected irrespective of study intervention discontinuation or participant's request to discontinue study procedures. All participants who have not withdrawn consent for further participation in the study should be followed for survival until the end of the study. OS for participants not known to have died are censored on the date of last known alive.

OS time will be estimated using the same Kaplan-Meier method and displayed graphically as described for PFS in Section 8.2.2.1. Median OS and 2-sided 95% CI will be provided. The OS rate at 6, 9, 12, 18, and 24 months will be estimated with corresponding two-sided 95% CIs.

Frequency (number and percentage) of participants with death events and censoring reasons will be presented by cohort along with the overall event and censor rates. The event and censoring reasons are as follows:

- Death;
- Alive (Ongoing and no death);

- Withdrawal of consent;
- Lost to follow-up.

The OS time or censoring time and the reasons for censoring will also be presented in a listing. The mITT Analysis will be used.

8.2.2.3. Time to Response (TTR)

In TTR analysis, TTR is defined, for participants with an objective response per IMWG criteria (i.e., subjects whose BOR are progressive disease, clinical relapse, stable disease, minimal response or deaths are excluded), as the time from the date of first dose to the first documentation of objective response that is subsequently confirmed. TTR will be calculated in days as follows:

$$\text{TTR (days)} = [\text{date of first objective response} - \text{date of first dose} + 1]$$

TTR will be summarized using simple descriptive statistics (mean, standard deviation, minimum, median, and maximum). **Censoring:** Subjects will be censored same as censoring for primary definition of progression free survival (PFS) used in the study. This will be calculated on all responding subjects.

8.2.2.4. Time to Complete Response (TTCR)

TTCR is defined, for participants with an objective response per IMWG criteria is CR or sCR, as the time from the date of first dose to the first documentation of sCR or CR that is subsequently confirmed. TTCR will be calculated in days as follows:

$$\text{TTCR (days)} = [\text{date of first CR or sCR} - \text{date of first dose} + 1]$$

TTCR will be summarized using simple descriptive statistics (mean, standard deviation, minimum, median, and maximum). **Censoring:** Subjects without response will be censored same as censoring for primary definition of progression free survival (PFS) used in the study. This will be calculated on all subjects with objective response of CR or sCR.

8.2.2.5. Time to VGPR or better (TTVGPR)

TTVGPR or better is defined, for participants with an objective response per IMWG criteria is VGPR, CR or sCR, as the time from the date of first dose to the first documentation of VFPR, CR or sCR that is subsequently confirmed. This will be calculated in days as follows:

$$\text{TTVGPR (days)} = [\text{date of first VGPR, CR or sCR} - \text{date of first dose} + 1]$$

TTVGPR or better will be summarized using simple descriptive statistics (mean, standard deviation, minimum, median, and maximum). **Censoring:** Subjects without response will be censored same as censoring for primary definition of progression free survival (PFS) used in

the study. This will be calculated on all subjects with objective response of VGPR, CR or sCR.

8.2.2.6. Duration of Response (DoR)

DoR is defined, for participants with an objective response per IMWG criteria, as the time from the first documentation of objective response that is subsequently confirmed, until PD per IMWG criteria, or death due to any cause, whichever occurs first. It will be calculated as follows:

$$\text{DoR (months)} = [\text{date of event or censoring} - \text{first date of objective response} + 1] / 30.4375$$

The censoring rules for DoR are as described for PFS in Section 8.2.2.1, except that participants will not be censored for inadequate baseline assessment or for no adequate post-baseline assessment, as only participants with an objective response are included in the analysis of DoR.

If at least 3 participants achieve an objective response and subsequently have an event, DoR will be estimated using the same Kaplan-Meier method as described for PFS in Section 8.2.2.1 and displayed graphically where appropriate. Otherwise, only listings will be provided.

The DoR rate at 3, 6, 9, 12 and 18 months (and in subsequent 6-month increments while there are participants still at risk) will be estimated with corresponding two-sided 95% CIs.

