3.4. Recommended Phase 2 Dose (RP2D) Definition

Based on preliminary safety, efficacy, PK, and pharmacodynamics data from Part 1 (monotherapy dose escalation), a dose of 1000 µg/kg SC weekly has been selected as the RP2D for PF-06863135 as a single agent. Briefly, single-agent anti-myeloma activity has been observed at doses \geq 215 µg/kg SC with an acceptable safety profile across all dose levels. The overall response rate (ORR) for the 215, 360, 600, and 1000 µg/kg SC dose levels was 75% (3/4), 75% (3/4), 66.7% (4/6) and 83% (5/6), respectively. In addition, preliminary exposure-efficacy analyses indicated that higher PF-06863135 exposure (average concentration at steady state) may be associated with higher probability of objective response, especially in patients with high baseline soluble BCMA. Overall, the data support 1000 µg/kg SC weekly as a tolerable dose that provides clinical benefit for the majority of patients with relapsed or refractory MM, including those with high baseline soluble BCMA.

Although only Grade 1 or Grade 2 CRS was reported during dose escalation, 2 of 6 patients experienced Grade 1 CRS events that lasted for 9 days with the first dose of 1000 µg/kg. The longest duration of CRS in the 600 µg/kg SC cohort was 4 days, which occurred in 1 patient and was Grade 1. Therefore, Part 1.1 of this study evaluates whether the duration of CRS can be mitigated by a single priming dose of 600 µg/kg given one week prior to 1000 µg/kg maintenance dosing (see [Section 1.2.9.6](#) for rationale). Based on preliminary safety data from Part 1.1, administration of a priming dose (600 µg/kg) reduces duration of CRS associated with subsequent maintenance dosing (1000 µg/kg). Therefore, a priming strategy will be adopted for both PF-06863135 monotherapy and combination therapy in this study as well as other studies.

For monotherapy dosing with PF-06863135, the RP2D of 1000 µg/kg will be administered as a fixed dose of 76 mg SC weekly (see [Section 1.2.9.4](#) for rationale) following a single priming dose of 44 mg (fixed dose equivalent of 600 µg/kg) administered one week before initiation of maintenance dosing.

The combination RP2D for PF-06863135 will be determined separately for each combination therapy.

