9.4. Efficacy Analysis

In this First in Patient study, anti-myeloma activity is a secondary objective in Part 1 dose escalation. Objective response rate (ORR) and duration of response (DOR) are primary objectives in Part 2 dose expansion. Other efficacy endpoints are secondary objectives in Part 2. The analysis population is defined in [Section 9.1](#) Analysis Sets.

Imaging studies, relevant laboratory assessments, and bone marrow pathology may be collected to support independent central review for efficacy endpoints.

PF-06863135

C1071001

Final Protocol Amendment 9, 28 March 2023

Disease response will be presented in the form of patient data listings that include, but are not limited to starting dose, disease response at each visit, and best overall response. In addition, progression date, death date, date of first response and last disease assessment date, and date of last contact will be listed.

Best overall response (BOR) will be assessed based on reported overall responses at different evaluation time points using IMWG response criteria (see [Appendix 2](#)).^{4,5}

- **Complete Response** will encompass confirmed stringent Complete Response (sCR) and Complete Response (CR).
- **Overall Response (OR)** will encompass confirmed sCR, CR, VGPR (very good partial response) and partial response (PR).
- **Clinical Benefit (CB)** will encompass confirmed sCR, CR, VGPR, PR and MR.

Progression -free survival (PFS) is the time from start date of study treatment to date of first documentation of progression, or death due to any cause. Progression is defined as the appearance of local, regional or distant disease of the same type after complete response or progression of pre-existing lesions. It does not include second primary malignancies of unrelated types.

Overall survival (OS) is the time from start date of study treatment to date of death due to any cause.

Duration of Complete Remission is defined for patients with confirmed complete response (sCR, CR) as the time from the first documentation of complete response to the first documentation of objective tumor progression or to death due to any cause, whichever occurs first.

Duration of Response (DOR) is defined for patients with confirmed objective response (as defined above in overall response) as the time from the first documentation of objective tumor response to the first documentation of objective tumor progression or to death due to any cause, whichever occurs first.

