8.2.2. Efficacy Analyses

No formal hypothesis testing will be performed on analysis of efficacy endpoints.

Efficacy analysis will be summarized by dose cohorts. Analysis of progression free survival and time to progression are defined as time from the date of first dose. Summaries of the n and % of subjects with PFS, and TTR and data listing by tumor type and dose will be generated. If applicable, the PFS may also be summarized using the Kaplan-Meier method at all or some of the following timepoints:

- OS at 6, 9, 12, 18, 24 months timepoints
- PFS, DOR, DoSD and DoCR at 3, 6, 9, 12, 18 months timepoints
- Reverse KM Follow-up probability is 3, 6, 9 months timepoints

The 95% confidence intervals will be generated. Confidence intervals for medians and quartiles will be based on the Brookmeyer-Crowley method. Confidence intervals for the estimated probability of an event at a particular time point will be generated using the Greenwood formula. Duration of response will be summarized with number of responders, number and percentage of event/censorship, mean, standard deviation, minimum, maximum and median of duration in unit of months. ORR and CBR will be summarized by number of subjects meeting respective criteria, percentage. The 95% confidence intervals will be generated for PFS, TTR, ORR, and CBR. Definitions of PFS, TTR, DoR, ORR, and CBR are outlined below.

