8.2.2.7. Duration of sCR or CR (DoCR)

DoCR is the time from first observation of sCR or CR to the time of disease progression, or death due to any cause. The censoring rules for DoCR are the same as those for PFS outlined in Section 8.2.2.1. This will be calculated on responding subjects with confirmed responses of CR or sCR.

DoCR is defined, for participants with a sCR or CR per IMWG criteria, as the time from the first documentation of sCR or CR that is subsequently confirmed, until PD per IMWG criteria, or death due to any cause, whichever occurs first. It will be calculated as follows:

$$\text{DoCR (months)} = [\text{date of event or censoring} - \text{first date of CR or sCR} + 1] / 30.4375$$

The censoring rules for DoCR are as described for DOR in Section 8.2.2.4.

If at least 3 participants achieve a CR or sCR and subsequently have an event, DoCR will be estimated using the same Kaplan-Meier method as described for DOR in Section 8.2.2.4 and displayed graphically where appropriate. Otherwise, only listings may be provided.

The DoCR rate at 3, 6, 9, 12 and 18 months will be estimated with corresponding two-sided 95% CIs.

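### The Kaplan-Meier estimate of duration of response and of complete response is conditional on at least 3 events among responders, so small, early or very durable cohorts can lose it, and SAP sections disagree on what such cohorts receive

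*SAP*

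**What the plan says.** Protocol 9.4 gives duration of response (DoR) its standing: "Objective response rate (ORR) and duration of response (DOR) are primary objectives in Part 2 dose expansion". In Part 1 it is a secondary endpoint.

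SAP 8.2.2.6 sets the rule: "If at least 3 participants achieve an objective response and subsequently have an event, DoR will be estimated using the same Kaplan-Meier method". If the count is not met, "Otherwise, only listings will be provided". SAP 8.2.2.7 repeats the threshold for duration of complete response (DoCR): "If at least 3 participants achieve a CR or sCR and subsequently have an event". There the fallback is weaker still, since listings are only optional. Neither section gives a reason for the number 3.

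Two other statements carry no event condition. The closing paragraph of 8.2.2.6 provides for estimates with confidence intervals of "The DoR rate at 3, 6, 9, 12 and 18 months (and in subsequent 6-month increments while there are participants still at risk"). The general text in SAP 8.2.2 says "Duration of response will be summarized with number of responders, number and percentage of event/censorship", followed by the mean, standard deviation, minimum, maximum and median. The reporting unit is also set there: "Efficacy analysis will be summarized by dose cohorts".

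SAP 8.2.2.1 (PFS), 8.2.2.2 (OS) and 8.2.2.10 (duration of stable disease) set no minimum number of events.

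**The concern.** Whether a cohort gets a curve depends on how many of its responders have already progressed or died. Take two cohorts with the same number of responders. If three have relapsed in one, it gets a curve and, where estimable, a median. If none has relapsed in the other, it gets listings, although it has the better result. A Kaplan-Meier curve and landmark rates can be computed with 0, 1 or 2 events; the median is then simply not reached.

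Two things are at stake. A reader who looks across the cohorts that have curves sees a set selected toward shorter durations. And two programmers could produce different tables for a Part 2 primary endpoint, because 8.2.2 and the landmark sentence in 8.2.2.6 can be read as applying to every cohort while the sentence before the landmark paragraph restricts the output to listings.

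**Working it through.** **The plan's own figures.** The 3-event rule has no stated figure to reproduce. The responder numbers for Part 2 come from Protocol 9.3, and those figures do reproduce under a Beta(0.5, 0.5) prior. For 12/20, the probability that the rate is at least 50% is 0.8142 (stated 0.814), and that it is below 30% is 0.0026 (stated 0.003). For 14/20 the results are 0.8184 (stated 0.818) and 0.0001 (stated 0.0001).

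**Inputs.**
- Median DoR of 11.6 months, 95% CI 7.2 to not estimable (Protocol 1.2.3.2).
- Responders by dose at 215, 360, 600 and 1000 µg/kg: "75% (3/4), 75% (3/4), 66.7% (4/6) and 83% (5/6), respectively" (Protocol 3.4, preliminary data).
- Part 2A enrolled 15 (Protocol 1.2.3.1). At the pooled response rate of 63.4% that is 0.634 × 15 = 9.5, or about 10 responders.
- Follow-up to 24 months (SAP 2.1) or about 30 months (Protocol 3.1) after the last patient's first treatment.
- Assumptions: exponential durations, and follow-up counted from first response. Medians of 24 and 36 months are assumed, to show the range.

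**Formula with equal follow-up T.** The chance that a responder has an event by T is p(T) = 1 − 2^(−T/11.6). The number of events K among r responders is binomial(r, p(T)). The cohort gets an estimate if K ≥ 3. Among cohorts that pass, the mean rate at landmark L is 1 − E[K | K ≥ 3] × p(L) / (p(T) × r).

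**Worked case, r = 3.** p(24) = 0.762, p(30) = 0.833 and p(9) = 0.416, so the true 9-month rate is 0.584. All three responders must have an event, so the pass probability is 0.762³ = 0.44 at 24 months and 0.833³ = 0.58 at 30 months. The mean 9-month rate among those that pass is 1 − 0.416/0.762 = 0.45 and 1 − 0.416/0.833 = 0.50.

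| Responders | Follow-up (months) | Gets an estimate | Mean 9-month rate shown | True |
|---|---|---|---|---|
| 3 | 12 | 13% | 19% | 58% |
| 4 | 12 | 33% | 35% | 58% |
| 5 | 12 | 52% | 44% | 58% |
| 3 | 24 to 30 | 44% to 58% | 45% to 50% | 58% |
| 4 | 24 to 30 | 76% to 87% | 53% to 56% | 58% |
| 5 | 24 to 30 | 91% to 96% | 56% to 58% | 58% |
| 9 | 24 to 30 | at least 99.9% | 58% | 58% |

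**Simulation with staggered censoring.** There were 200,000 runs per scenario, with censoring uniform over the stated range. Each cell gives the probability of fewer than 3 events.

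| Responders, follow-up (months) | Median 11.6 | Median 24 | Median 36 |
|---|---|---|---|
| 4, 24–30 | 0.180 | 0.625 | 0.816 |
| 10, 24–30 | 0.000 | 0.031 | 0.160 |
| 12, 24–30 | 0.000 | 0.009 | 0.079 |
| 12, 6–12 | 0.071 | 0.460 | 0.708 |

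Among cohorts that pass, the mean estimate differs from the truth as follows, for medians of 11.6, 24 and 36 months:
- 4 responders, 24–30 months, rate at month 12: −0.047, −0.143, −0.194.
- 12 responders, 24–30 months, rate at month 12: about 0, −0.002, −0.012.
- 12 responders, 6–12 months, rate at month 6: −0.016, −0.064, −0.091.

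With no condition, the mean estimate matches the truth to within about 0.001 in every scenario. The shortfall therefore comes from the selection and not from the estimator.

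**The case against.** The case for leaving the rule alone has several parts.

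- **Cohorts below the threshold are not left out.** A reader might infer that durable cohorts go unreported. The documents do not support that: 8.2.2.6 requires listings, and 8.2.2 asks for counts of responders, events and censorings and a median. This stands, with one limit. 8.2.2 does not say how censored durations enter its mean and median, so that summary does not replace a Kaplan-Meier estimate.
- **The Part 2 primary endpoint is hardly touched at the end.** With about 10 or more responders, 24 to 30 months of follow-up and the documents' own median, the threshold is essentially always met. This stands. The large effects concern small Part 1 dose cohorts, where DoR is secondary, or early cuts. SAP 2 permits an interim report at any time but schedules none.
- **No decision rests on it.** SAP 6.5 plans no comparison between dose groups, 8.1 calls the summaries non-inferential, and 8.2.2 has no hypothesis tests. This stands, so a claim that a planned dose comparison is biased would go too far. A reader may still set the cohorts side by side.
- **A minimum is sensible in tiny cohorts.** Agreed, but a minimum number of responders serves that purpose without depending on the outcome.
- **The counts in Protocol 3.4 are preliminary.** Agreed. The statement that the 215 and 360 µg/kg cohorts, with 3 responders each, would need every responder to relapse or die is conditional on those counts.

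**Conclusion.** The point holds in a limited form. The condition in 8.2.2.6 and 8.2.2.7 depends on the outcome, is unexplained, is not used for PFS, OS or duration of stable disease, and is inconsistent with ungated text in 8.2.2 and in 8.2.2.6 itself.

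At a median of 11.6 months and full follow-up, its effect is large only in cohorts of 3 responders. With 4 or 5 responders the mean 9-month rate shown is about 1 to 5 percentage points low (for example 53.0% against 58.4% with 4 responders at 24 months). With 9 or more it is about zero. It grows at early cuts and if responses last much longer than 11.6 months. These sizes rest on exponential durations and on follow-up counted from first response; the longer medians are assumptions.

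Two stronger readings should be resisted. The first is that Kaplan-Meier estimates of DoR in this trial are biased downward: within a cohort they are not, and the shortfall appears only across the set of cohorts that pass. The second is that the final Part 2 result is compromised: at the expected number of responders, the observed median and full follow-up, it is not.

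**What to change.** In SAP 8.2.2.6 and 8.2.2.7, make the condition depend on the number of responders (complete responders for DoCR), for example at least 3. For each cohort that qualifies, report the numbers of responders, events and censored patients, Kaplan-Meier landmark rates with confidence intervals, and the median, shown as not reached where that applies. Keep listings for smaller cohorts, and make them definite for DoCR as well. Align SAP 8.2.2 and the landmark sentences with this rule, so that one text decides what each cohort receives.

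The cost is one changed sentence in each of two sections plus the alignment in 8.2.2. The downside is wide intervals in small cohorts, which reflect how little such cohorts can show.

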8.2.2.7. Duration of sCR or CR (DoCR)

DoCR is the time from first observation of sCR or CR to the time of disease progression, or death due to any cause. The censoring rules for DoCR are the same as those for PFS outlined in Section 8.2.2.1. This will be calculated on responding subjects with confirmed responses of CR or sCR.

DoCR is defined, for participants with a sCR or CR per IMWG criteria, as the time from the first documentation of sCR or CR that is subsequently confirmed, until PD per IMWG criteria, or death due to any cause, whichever occurs first. It will be calculated as follows:

$$\text{DoCR (months)} = [\text{date of event or censoring} - \text{first date of CR or sCR} + 1] / 30.4375$$

The censoring rules for DoCR are as described for DOR in Section 8.2.2.4.

If at least 3 participants achieve a CR or sCR and subsequently have an event, DoCR will be estimated using the same Kaplan-Meier method as described for DOR in Section 8.2.2.4 and displayed graphically where appropriate. Otherwise, only listings may be provided.

The DoCR rate at 3, 6, 9, 12 and 18 months will be estimated with corresponding two-sided 95% CIs.

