An adequate post-baseline assessment is defined as an assessment where a response of sCR, CR, VGPR, PR, MR, SD, Relapse or PD can be determined based on IMWG response criteria for multiple myeloma. Subjects with no baseline disease assessment (including subjects with an inadequate baseline assessment) or with no adequate post-baseline disease assessments within 46 days for cohorts with 21 day cycles and 60 days for cohorts with 28 day cycles after the date of first dose will be censored on the date of first dose, unless the subject dies within 46 days for cohorts with 21 day cycles and 60 days for cohorts with 28 day cycles of the date of the first dose, in which case, death will be an event on date of death. Subjects will be considered to have progressive disease if they meet the criteria for progression by a variable that was not considered measurable at baseline.

Events and censoring rules are summarized in Table 4.

Table 4. Progression Free Survival

Situation	Date of Progression/Censoring¹	Outcome
Inadequate baseline assessment	First dosing date in Cycle 1 (or Cycle 0 for priming cohorts)	Censored
No on-study assessments	First dosing date in Cycle 1 (or Cycle 0 for priming cohorts)	Censored
Alive, on treatment ² and no Progression	Date of last objective tumor assessment ³	Censored
New anti-cancer therapy	Date of last adequate disease assessment that documented no progression prior to new anti-cancer therapy	Censored
Progression Documented on or between scheduled tumor assessments prior to treatment discontinuation ²	Date of first objective tumor assessment showing objective progression	Progressed (Event)
Withdrawal of consent prior and refusal to follow-up	Date of last objective tumor assessment prior to	Censored

	discontinuation ²	
Treatment discontinuation for undocumented progression, toxicity or other reason	Date of last objective tumor assessment prior to discontinuation ²	Censored
Death prior to first planned tumor assessment	Date of death	Death (Event)
Death without objective progression prior to treatment discontinuation ²	Date of death	Death (Event)
Death or progression after 2 or more missed tumor assessments ⁴	Date of last objective tumor assessment prior to the event	Censored
Lost to follow-up	Date of last objective tumor assessment ³	Censored

1. For date of censorship, if a tumor assessment takes place over a number of days (e.g., superficial lesions one day, scans another), the last date is used as the assessment date.

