8.2.2.10. Duration of Stable Disease (DoSD)

The DoSD is defined for patients with stable disease as the time from the first documentation of objective stable disease to the first documentation of objective tumor progression or to death due to any cause, whichever occurs first. It will be calculated as follows:

$$\text{DoSD (months)} = [\text{date of event or censoring} - \text{first date of SD} + 1] / 30.4375$$

The censoring rules for DoSD are as described for PFS in [Section 8.2.2.1](#). This analysis will include only participants with confirmed stable disease or better. The DoSD rate at 3, 6, 9, 12 and 18 months will be estimated with corresponding two-sided 95% CIs.

For subjects with no adequate baseline assessment but with post-baseline assessments which can confirm SD, subjects will be censored to first dose date, then we will calculate DoSD= max ((date of event or censoring – first date of SD + 1) , 1). So DoSD will be 1 day instead of negative value.

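### SAP 8.2.2.7 gives two conflicting censoring rules for duration of complete response, and the PFS one can return a negative duration

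*SAP*

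**What the plan says.** SAP Section 8.2.2.7 states the DoCR censoring rule twice.

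- First paragraph: "The censoring rules for DoCR are the same as those for PFS outlined in Section 8.2.2.1".
- After the formula: "The censoring rules for DoCR are as described for DOR in Section 8.2.2.4". The same section number is cited again for the Kaplan-Meier method.

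Section 8.2.2.4 is time to complete response. DoR is Section 8.2.2.6, which adopts the PFS rules "except that participants will not be censored for inadequate baseline assessment or for no adequate post-baseline assessment", on the ground that only responders are analysed.

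The PFS section (8.2.2.1) treats such patients differently. A patient with no adequate baseline, or with no adequate post-baseline assessment within 46 days (21-day cycles) or 60 days (28-day cycles), "will be censored on the date of first dose, unless the subject dies within 46 days for cohorts with 21 day cycles", with the matching 60-day limit for 28-day cycles. Table 4 likewise gives the first dosing date as the censoring date for an inadequate baseline.

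For duration of stable disease (DoSD), Section 8.2.2.10 keeps the PFS rules, notes that a patient without an adequate baseline would get a negative time, and sets a minimum: "So DoSD will be 1 day instead of negative value". Section 8.2.2.7 has no such minimum.

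**The concern.** A complete responder with an inadequate baseline, or with a late first adequate assessment, has an ordinary positive remission time under one sentence and a censoring date before the remission started under the other. A negative time cannot enter a Kaplan-Meier estimate, and the SAP does not say whether to drop it, recode it or set it to a minimum. Two programmers following the text could produce different DoCR results.

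The choice also affects whether an estimate is produced. Section 8.2.2.7 runs Kaplan-Meier only if at least 3 participants reach CR or sCR and then have an event. Under the PFS rule, an inadequate-baseline complete responder who later progresses counts as censored, so a cohort could fall below 3 events and get listings only. Cohorts are small: Protocol Section 1.2.3.1 reports 15 patients in Part 2A, 4 in Part 1C and 9 in Part 1D at the June 2022 cutoff.

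The protocol does not settle the matter. Its Section 9.4 defines DoCR without a censoring rule, and SAP Section 2 says the SAP supersedes the protocol's statistical text.

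**Working it through.** The documents give no figure to reproduce here, so the check is date arithmetic on the SAP's own formula.

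**Inputs**

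- Formula (SAP 8.2.2.7): DoCR in months = (date of event or censoring - date of first CR or sCR + 1)/30.4375.
- Censoring date under the PFS rule with an inadequate baseline (SAP 8.2.2.1 and Table 4): first dose, taken as study Day 1.
- Date of first complete response: not given in the documents, so assumed over a range. The range starts at Cycle 2 Day 1, the earliest scheduled laboratory disease assessment after treatment starts. That is Day 22 with 21-day cycles, Day 29 with 28-day cycles, and Day 36 with a one-week priming cycle followed by a 28-day cycle.
- Last adequate assessment, no event: Day 400, assumed, for comparison only.

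**PFS rule:** (1 - CR day + 1)/30.4375. **DoR rule:** (400 - CR day + 1)/30.4375.

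| First CR (study day) | PFS rule, days | PFS rule, months | DoR rule, days | DoR rule, months |
|---|---|---|---|---|
| 22 | -20 | -0.66 | 379 | 12.45 |
| 29 | -27 | -0.89 | 372 | 12.22 |
| 36 | -34 | -1.12 | 365 | 11.99 |
| 64 | -62 | -2.04 | 337 | 11.07 |
| 92 | -90 | -2.96 | 309 | 10.15 |
| 183 | -181 | -5.95 | 218 | 7.16 |

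The PFS-rule value is 2 minus the CR day. It is therefore negative from Day 3 onward, which covers every scheduled post-baseline assessment.

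**Second route to a negative value.** The PFS rule also censors at first dose when there is no adequate post-baseline assessment within 46 or 60 days. If the limit is read as a study day, a complete response first documented on Day 47 gives 1 - 47 + 1 = -45 days (-1.48 months), and on Day 61 gives 1 - 61 + 1 = -59 days (-1.94 months). Counting the window from the day after first dose moves each by one day.

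**Where the rules agree.** For a complete responder with an adequate baseline and a timely first assessment, the two rules give the same result. A death within 46 or 60 days of first dose is an event under the PFS text, so it does not lead to this problem.

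**The case against.** The strongest reply is that the intended rule can be worked out. The fuller definition in Section 8.2.2.7, with the formula and the confirmation requirement, names DoR. The reason Section 8.2.2.6 gives for its exception applies equally to complete responders. Section 8.2.2.4 contains no Kaplan-Meier method, so the number is evidently a slip. Its PFS pointer covers only patients without a response, so it gives no rule for complete responders. On this reading, the fault is a leftover sentence and a wrong number, and the negative value arises only if an analyst follows the PFS sentence.

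The affected group should also be small. Measurable disease is an inclusion criterion (Protocol Section 4.1), screening falls within 28 days before first dose, and the disease laboratory tests are scheduled at screening and on the first dosing day. An inadequate baseline therefore implies some departure from the schedule or eligibility. The analyses are descriptive, and DoR, a Part 2 primary endpoint, already has the correct exception.

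All of this bears on size, and it stands. It does not remove the conflict. The PFS sentence is an unqualified instruction in the governing document, and the sentence that should override it carries a wrong section number. The SAP also expects such patients to occur, because it writes a rule for them under DoSD.

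**Conclusion.** The concern holds: Section 8.2.2.7 is wrong as written. It gives two incompatible censoring rules, and one of them yields an impossible value. For an inadequate-baseline complete responder first in CR on Day 64, the result is -2.04 months under the PFS sentence. Under the DoR rule it is 11.07 months if the last adequate assessment is on Day 400. Both dates are assumptions; the sign does not depend on them, because any first CR from Day 3 onward is negative under the PFS sentence.

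The practical weight is low. It is confined to confirmed CR or sCR patients with an inadequate baseline or a late first adequate assessment, on a secondary endpoint. The documents give neither the number of such patients nor the number of complete responders per cohort, so the effect on a reported median or rate cannot be computed.

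**What to change.** In SAP Section 8.2.2.7:

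1. Delete the first-paragraph sentence that applies the PFS censoring rules.
2. Change both references to Section 8.2.2.4 (censoring and Kaplan-Meier method) to Section 8.2.2.6.
3. State that complete responders are not censored for an inadequate baseline or for no adequate post-baseline assessment.

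The third change closes both routes to a negative value. Copying the DoSD minimum would not be a good substitute: it would record 1 day (1/30.4375 = 0.03 months) for a patient whose remission was observed for far longer.

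The cost is a few sentences in the SAP, with no new data collection.
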